7.3.2 Other Restrictions and Precautions

Patients being treated with anti-cancer immunotherapy are permitted.

7.4 Treatment Compliance

Treatment compliance with all study-related medications should be emphasized to the subject by the site personnel. Compliance with BMS-986253 will be documented in the medical record and monitored by the principal investigator or its designee.

7.5 Randomization and Blinding

Patients will be randomized 2:1 (anti-IL8: standard of care) in “real-time”. If the subject’s eligibility status is confirmed, the statistician will send the randomization assignment based on the pre-generated randomization scheme.

This is an open-label study.

7.6 Duration of Therapy

In the absence of treatment discontinuation due to adverse events, treatment may continue for up to 4 weeks or until one of the following criteria applies:

- Intercurrent illness that prevents further administration of treatment
- Unacceptable adverse events(s)
- Patient decides to withdraw from the study
- General or specific changes in the patient's condition render the patient unacceptable for further treatment in the judgment of the investigator
- Patient has been discharged from the hospital

At the end of the study period, Bristol-Myers Squibb Company will not continue to supply study drug to subjects/investigators unless the Sponsor-Investigator chooses to extend their study and such extension is approved by Bristol Myers Squibb Company. The investigator is responsible to ensure that the subject receives appropriate standard of care or other appropriate treatment in the independent medical judgement of the Investigator to treat the condition under study.

7.7 Duration of Follow Up

Following completion of therapy, patient will have follow up by phone every 30 days for the first 100 days following the last dose of therapy. Patients will then have follow up by phone every 90 days (+/- 30 days) for up to 1 year. In addition, patients will be assessed 28 days (+/- 2 days) following start of treatment whether they are discharged or in the hospital. Participants who discontinue study treatment must continue to be followed for collection of outcome and/or survival follow-up data as required and in line with **Section 4.1** until death or the conclusion of the study.

7.8 Criteria for Removal from Study

Patients will be removed from study when any of the criteria listed in Section 8.6 applies. The reason for study removal and the date the patient was removed will be documented in the Case Report Form.

DOSING DELAYS/ DOSE MODIFICATIONS

7.9 **Criteria and Procedures for Dose Modifications and Interruptions**

Dose escalation/reduction is not permitted in this study in order to allow better evaluation of the safety and efficacy. However, if toxicities occur, subsequent doses of BMS-986253 should follow the below guidelines:

Toxicity	Grade	Hold Treatment (Y/N)	Timing of Treatment Restart	Dose Schedule for Treatment Restart	Discontinue Subject
	1, 2	No	N/A	N/A	N/A

Hematologic Toxicity	3, 4	Yes	Toxicity resolves to \leq Grade 1 or baseline	Restart at same dose. However, for all Grade 4 hematologic toxicities, treatment may not be restarted.	Toxicity does not resolve to \leq Grade 1 or baseline by the time of next treatment dose. Permanent discontinuation should be considered for any severe or life-threatening event.
Non-Hematologic Toxicity Note: Exception to be treated similar to Grade 1 toxicity: - Grade 2 fatigue - Grade 3 rash in patients who have not experienced a grade 3 drug-related skin AE	1	No	N/A	N/A	N/A
	2	Consider holding for persistent symptoms	Toxicity resolves to \leq Grade 1 or baseline	Restart at same dose	Toxicity does not resolve to \leq Grade 1 or baseline by the time of next treatment dose. Permanent discontinuation should be considered for any severe or life-threatening event
	3	Yes	Toxicity resolves to \leq Grade 1 or baseline	Restart at same dose	Toxicity does not resolve to \leq Grade 1 or baseline by the time of next treatment dose. Permanent discontinuation should be considered for any severe or life-threatening event
	4	Yes	Discontinue treatment	Treatment may not be restarted	Yes.

Criteria to resume treatment:

Subsequent dosing with study therapy may resume once AEs resolve to Grade 1 or baseline.

Participants experiencing AEs not meeting criteria for permanent discontinuation as outlined in **Section 5.5** may resume treatment with study medication under the following criteria:

- Participants may resume treatment with study treatment when the drug-related AE(s) resolve to Grade \leq 1 or baseline value, with the following exceptions:
 - Participants may resume treatment in the presence of Grade 2 fatigue.
 - Participants who have not experienced a Grade 3 drug-related skin AE may resume treatment in the presence of Grade 2 skin toxicity.
 - Participants with Grade 2 uveitis, episcleritis, iritis, eye pain, or blurred vision (except for patients that do not respond to topical therapy and does not improve to Grade 1 severity within the re-treatment period OR requires systemic treatment).
- For participants with Grade 2 AST, ALT, or total bilirubin elevations, dosing may resume when laboratory values return to baseline and management with corticosteroids (if needed) is complete.
- Participants with combined Grade 2 AST/ALT and total bilirubin values with symptomatic liver inflammation (eg, right upper quadrant tenderness, jaundice) should have treatment permanently discontinued.

Exceptions to permanent discontinuation criteria:

The following exceptions to permanent discontinuation will apply:

- Grade 3 diarrhea, nausea, vomiting, or abdominal pain that returns to Grade 1 or baseline within 3 days with medical intervention.

- Grade 3 pruritus or rash that returns to Grade 1 or baseline within 7 days with medical intervention.
- Isolated Grade 3 or 4 electrolyte imbalances/abnormalities that are not associated with clinical sequelae and are corrected with supplementation/appropriate management within 3 days of their onset.
- Grade 4 neutropenia < 7 days in duration.
- Grade 4 lymphopenia or leukopenia.
- Grade 3 or 4 increase in amylase or lipase that is not associated with clinical or radiographic evidence of pancreatitis.
- Grade 3 infusion reactions that return to Grade 1 in < 6 hours.
- Grade 3 fever not associated with hemodynamic compromise (eg, hypotension, clinical, or laboratory evidence of impaired end-organ perfusion).
- Grade 3 tumor flare (defined as pain, irritation, or rash that localizes to sites of known or suspected tumor).
- Grade 3 fatigue.
- Grade 3 or 4 drug-related endocrinopathy AEs, such as adrenal insufficiency, adrenocorticotropic hormone, hyper- or hypothyroidism, or glucose intolerance, which resolve or adequately controlled with physiologic hormone replacement (corticosteroids, thyroid hormones) or glucose-controlling agents, respectively, may not require discontinuation after discussion with and approval from the Sponsor-Investigator.
- Any AE, laboratory abnormality, or concurrent illness, which, in the judgment of the investigator, presents a substantial clinical risk to the participant with continued study treatment dosing.

Even if the criteria to resume treatment are met, the consideration to re-initiate study therapy under the following exception will be made on a case by case basis after considering the overall benefit/risk profile, and in consultation between the investigator and the Sponsor. Any AE with clinical risk will be assessed on a case by case basis with the investigator and the BMS Medical Monitor, to determine the risks and benefits of continuing on therapy following resolution versus discontinuing therapy permanently.

All participants who discontinue IP should comply with protocol specified follow-up procedures as outlined in **Section 5.5**. The only exception to this requirement is when a participant withdraws consent for all study procedures including post treatment study follow-up or loses the ability to consent freely (e.g., imprisonment, involuntarily incarceration for the treatment of either a psychiatric or physical illness). If study treatment is discontinued prior to the participant's completion of the study, the reason for the discontinuation must be documented in the participant's medical records and entered on the appropriate case report form (CRF) page.

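### Section 7.9 bars restart after grade 4 toxicity in its dose-modification table but exempts several grade 4 events from permanent discontinuation in its exceptions list, and does not say which governs

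*Combined protocol and SAP*

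**What the plan says.** Section 7.9 contains three pieces of text that bear on redosing after a grade 4 event.

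- **The table.** It is introduced with the statement that "if toxicities occur, subsequent doses of BMS-986253 should follow the below guidelines". The hematologic row covers grades 3 and 4 together and adds that "for all Grade 4 hematologic toxicities, treatment may not be restarted". The grade 4 non-hematologic row directs discontinuation, repeats that "treatment may not be restarted", and answers yes in the column on discontinuing the subject.
- **The exceptions list.** It opens with "The following exceptions to permanent discontinuation will apply". Five of its twelve items name grade 4 events: "Grade 4 neutropenia < 7 days in duration"; "Grade 4 lymphopenia or leukopenia"; "Isolated Grade 3 or 4 electrolyte imbalances/abnormalities that are not associated with clinical sequelae", if corrected within 3 days of onset; "Grade 3 or 4 increase in amylase or lipase that is not associated with clinical or radiographic evidence of pancreatitis"; and drug-related endocrinopathy that resolves or is controlled, subject to Sponsor-Investigator approval.
- **The closing consultation paragraph.** Even where the resumption criteria are met, re-initiation is weighed individually between the investigator and the Sponsor. Events with clinical risk are also assessed with the manufacturer's medical monitor.

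For the permanent-discontinuation criteria themselves, Section 7.9 points to Section 5.5.

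**The concern.** An investigator with a patient still in hospital at day 15 or day 29, after one of the listed grade 4 events, finds a bar on further dosing in the table and an exemption from that bar in the list. Two clinicians reading the section in good faith could reach different conclusions about whether redosing is open for discussion at all. The first stake is consistent handling of patient safety after events of the highest non-fatal grade. A lesser one is that it is unclear whether redosing such a patient, or withholding a dose, follows the protocol.

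**Working it through.** No figure in the plan is at issue and no arithmetic applies beyond counting. The check sets the two rules side by side and then looks for text that reconciles them.

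| Grade 4 event | Table row | Exceptions list | Strength of conflict |
|---|---|---|---|
| Lymphopenia or leukopenia | Hematologic: no restart | Exempt, no condition | Direct |
| Neutropenia | Hematologic: no restart | Exempt if under 7 days | Direct when the condition is met |
| Isolated electrolyte abnormality | Non-hematologic: no restart | Exempt if no sequelae and corrected within 3 days | Direct when the conditions are met |
| Amylase or lipase increase | Non-hematologic: no restart | Exempt if no evidence of pancreatitis | Direct when the condition is met |
| Drug-related endocrinopathy | Non-hematologic: no restart | May be exempt, with approval | Softer |

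The count is 2 hematologic items plus 3 non-hematologic items, 5 in all.

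Four places could resolve the conflict.

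1. **The table itself.** It carries its own exceptions where the drafters wanted them: a note treats grade 2 fatigue and a first grade 3 rash like grade 1. It has no grade 4 exception and no pointer to the list, and the hematologic restriction is worded to cover *all* grade 4 events.
2. **The list.** It does not say that it overrides the table. Elsewhere the drafters did align such rules: the exemption for a grade 3 infusion reaction that settles to grade 1 in under 6 hours appears both in Section 7.2 and in the list. The grade 4 items have no such match in the table.
3. **Section 5.5.** It provides for removal from study treatment for unacceptable toxicity, judged with the principal investigator. It has no criteria by grade, so it neither supports the table nor gives the list anything specific to modify.
4. **The closing consultation paragraph.** It assumes that a restart is possible once the criteria are met, which the table denies for grade 4. It does not say which text prevails.

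Two neighbouring entries add to the uncertainty. In the combined grade 3–4 hematologic row, the discontinuation column depends on failure to resolve before the next dose, although grade 4 is already barred from restart. And the last exception, an event judged to pose substantial clinical risk with continued dosing, reads as a reason to stop and not as an exception to stopping.

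On how often this could arise, eligibility (Section 5.1) requires an ANC above 500 cells/mm³ and sets no lymphocyte floor, and blood counts are taken daily in hospital (Section 10.2). Against that, Section 8.2 counts only new or worsening conditions as adverse events. Section 3.4.2 reports one grade 3 neutropenia in the combination study of 92 participants and no clinically significant neutropenia in earlier trials. Amylase and lipase are not in the protocol laboratory panel. No expected frequency can be derived from this.

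**The case against.** The best defence is that the list is an ordinary carve-out. It sits in the same section, is headed as exceptions and is stated to apply. Since Section 5.5 has no grade-based criteria, the table is the only grade-based bar that the grade 4 exceptions could modify; read otherwise, they would have no function. The table is introduced as guidelines, and the consultation paragraph requires a joint decision before redosing.

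Much of this stands. The carve-out is a plausible account of intent, and the consultation step is a real safeguard, so redosing does not turn only on which paragraph someone happens to read. But the carve-out does not deal with the word *all* in the hematologic row, and the consultation step gives those consulting no rule on precedence.

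A reader might infer three stronger things that the documents do not support.

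- **That the texts cannot both be obeyed.** They can: an exemption from permanent discontinuation permits a restart without requiring one, so withholding treatment breaches neither. The conflict is barred versus permitted, not two opposite commands.
- **That different sites would act differently.** This is a single-center trial. Any inconsistency would be between clinicians or between patients.
- **That per-protocol membership becomes undecidable.** Section 13.5.1 excludes relevant major deviations, gives lack of laboratory-confirmed infection as its example, and does not class redosing after a grade 4 event as one. It uses that set only for sensitivity analysis of the primary endpoint.

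**Conclusion.** The inconsistency is real and lies on the face of Section 7.9. Five list items naming grade 4 events meet a table that rules out a restart. The conflict is clearest for lymphopenia or leukopenia and for neutropenia under 7 days, conditional for electrolyte abnormalities and amylase or lipase increases, and softest for endocrinopathy.

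Its size cannot be expressed as a number of patients. The question arises only in the anti-IL-8 arm (92 planned) and only at the second dose, for patients still hospitalized, or the optional third. The sample size, error rate and primary test are untouched.

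The conclusion rests on reading the table's wording as a prohibition. The grade 4 non-hematologic row supports that reading, since it pairs the same wording with an instruction to discontinue.

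**What to change.** Reconcile the table, the exceptions list and the closing consultation paragraph of Section 7.9 so that each grade 4 event has one instruction. State the relationship explicitly, by a cross-reference from the table rows to the list or by a sentence giving the order of precedence, and say how the consultation step fits in. Correct the reference to Section 5.5 so that it leads to the actual discontinuation criteria. In the same pass, clarify the discontinuation cell of the combined grade 3–4 hematologic row and the last item of the exceptions list. Which rule applies to each event is for the sponsor's clinical team; this review takes no position on it.

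The cost is a protocol wording amendment with IRB approval. No design parameter, data collection or analysis changes.

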11.2.17 To characterize PK of BMS-986253

Will assess PK at screening, day 8, 15, 22, 29, and EOT by collection of serum at these time points when feasible. For patients ready for discharge prior to day 8, a serum sample should be collected, when feasible, prior to discharge.

Stopping Rules

The study may be discontinued by the data and safety monitoring committee (DSMC), the Food and Drug Administration (FDA), or other regulatory authorities. Any unforeseen deaths or serious adverse events may, after a discussion between the principal investigator, prompt an interruption to study accrual pending a full investigation into the circumstances surrounding the event.

Continuous Toxicity Monitoring

As this trial will be the first time an anti-IL-8 will be tested in patients with severe COVID-19, safety will be monitored on a continual basis. Sequential boundaries will be used to monitor dose-limiting toxicity rate.¹⁶ The accrual will be halted if excessive numbers of dose-limiting toxicities are seen, that is, if the number of dose-limiting toxicities is equal to or exceeds b_n out of n patients with full follow-up (see Table 3). This is a Pocock-type stopping boundary that yields the probability of crossing the boundary at most 0.05 when the rate of dose-limiting toxicity is equal to the acceptable rate of 30%. For the purposes of this stopping rule, dose-limiting toxicities will be defined as any treated related grade 3 or 4 toxicity.

Table 3. Toxicity Monitoring

Number of Patients, n	1	2	3	4	5	6-7	8-9	10-11	12-14	15-16	17-18	19-21	22-23	24-25	26-28	29-30	31-33	34-36	37-38
Boundary, b_n^*	-	-	-	4	5	6	7	8	9	10	11	12	13	14	15	16	17	18	19
Number of Patients, n	39-42-	44-	47-	50-	52-	55-	58-	60-	63-	66-	67-	71-	74-	77-	79-	82-	85-	98-	
	41	43	46	49	51	54	57	59	62	65	67	70	73	76	78	81	84	87	90
Boundary, b_n^*	20	21	22	23	24	25	26	27	28	29	30	31	32	33	34	35	36	37	38
Number of Patients, n	91-																		
	92																		
Boundary, b_n^*	39																		

*This boundary is equivalent to testing the null hypothesis, after each patient, that the event rate is equal to 30%, using a one-sided level 0.009 test.

For example, based on the boundaries above, if 12 out of the first 20 patients enrolled in the anti-IL-8 arm experience dose-limiting toxicities, the trial will be stopped for safety. In this case, the 95% exact confidence interval will be (0.36, 0.81), with the lower confidence limit exceeding the event rate (30%).

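### A note in the Section 7.9 table can be read as allowing BMS-986253 without a hold during a first Grade 3 rash, against the Grade 3 row and the resume criteria

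*Combined protocol and SAP*

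**What the plan says.** Section 7.9 of the combined protocol and SAP deals with rash in four places.

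- **Table, non-hematologic Grade 3 row.** Treatment is held and restarted at the same dose once the toxicity is at Grade 1 or lower, or at baseline. The subject is discontinued if this has not happened by the next dose.
- **Table, note to the non-hematologic rows.** Two items fall under "Exception to be treated similar to Grade 1 toxicity": Grade 2 fatigue, and "Grade 3 rash in patients who have not experienced a grade 3 drug-related skin AE". The Grade 1 row says not to hold and has no entry for restart or discontinuation.
- **Criteria to resume treatment.** The general rule is "Subsequent dosing with study therapy may resume once AEs resolve to Grade 1 or baseline". Listed exceptions include "Participants may resume treatment in the presence of Grade 2 fatigue" and "Participants who have not experienced a Grade 3 drug-related skin AE may resume treatment in the presence of Grade 2 skin toxicity". The list is introduced as applying to drug-related events.
- **Exceptions to permanent discontinuation.** These include "Grade 3 pruritus or rash that returns to Grade 1 or baseline within 7 days with medical intervention" and "Grade 3 fatigue".

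Outside Section 7.9, the stopping rule under Continuous Toxicity Monitoring in Section 11 states that "dose-limiting toxicities will be defined as any treated related grade 3 or 4 toxicity". Appendix A describes Grade 3 as severe or medically significant.

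**The concern.** The note and the resume criteria use the same patient history, no Grade 3 drug-related skin event, but reach different grades. The note lets dosing go ahead with a Grade 3 rash; the resume criteria stop at Grade 2. The note's condition is also hard to apply, because a drug-related Grade 3 rash is itself a Grade 3 drug-related skin event. One investigator may take the condition to mean no earlier event and give the dose. Another may count the current rash and hold.

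What is at stake is the safety of an individual patient and consistent decisions at the bedside. On the permissive reading, a treatment-related rash that the stopping rule counts as dose-limiting would be managed like a mild event, and the next 2400 mg infusion would be given. The count for the stopping rule is the same on either reading.

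**Working it through.** No figure in the plan needs to be reproduced. The main check is to set the rules side by side.

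| Place in Section 7.9 | Rash or skin toxicity | Fatigue |
|---|---|---|
| Table note (handled as Grade 1, no hold) | Grade 3 | Grade 2 |
| Criteria to resume | Grade 2 | Grade 2 |
| Exceptions to permanent discontinuation | Grade 3, if back to Grade 1 or baseline within 7 days | Grade 3 |

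**Two readings of the note.**

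1. *The condition means no earlier event.* A first Grade 3 rash, drug-related or not, goes to the Grade 1 row and is not held. This contradicts the Grade 3 row and exceeds the Grade 2 limit in the resume criteria.
2. *The current rash counts.* A drug-related Grade 3 rash removes the patient from the note, and the Grade 3 row applies. The note then covers only rash not attributed to the drug, and there is no conflict.

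One could try to rescue the first reading by saying that the note governs holding and the resume list governs restarting. Then a patient who was never held could be dosed at Grade 3, while a patient with the same history who was held could not restart above Grade 2. The plan gives no reason for such a difference.

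**How many patients.** Doses fall on Days 1, 15 and 29 (Section 7.1). A rash can matter only if it is present when the Day 15 dose, or the optional Day 29 dose, is due.

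Inputs from the documents:
- 92 patients are planned for the anti-IL-8 arm (Section 13.1).
- In CA027-001, 15 monotherapy participants had no related event above Grade 2 (Section 9.1.7).
- In CA027-002, with nivolumab, there were 92 participants. Among the most common related events, rash is listed at Grade 1 in 3, and only events with N > 2 are listed (Section 9.1.7).

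Assumptions, which the documents do not give:
- 0 to 2 Grade 3 rashes in CA027-002 fell below the listing threshold.
- A rash lasts 7 days with onset spread evenly over the 14-day interval, so 7/14 = 0.5 are present on Day 15.
- 25% to 100% of patients are still in hospital on Day 15.

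Range from the point estimates:
- At any time: (0 to 2)/92 × 92 = 0 to 2.0 patients.
- Present at Day 15 and in hospital: at most 2.0 × 0.5 × 1.00 = 1.0, so 0 to about 1.0 patient.

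Upper bound if the true count was zero in all 92 + 15 = 107 participants:
- Exact two-sided 95% limit: 1 − 0.025^(1/107) = 0.0339, or 3.4%.
- At any time: 92 × 0.0339 = 3.1 patients.
- Present at Day 15: 3.1 × 0.5 × 25%, 50% or 100% in hospital = 0.4, 0.8 or 1.6 patients.

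**The case against.** The strongest reply is that the second reading is the literal one. A patient with a drug-related Grade 3 rash has, in plain words, experienced such an event, so the exemption lapses and the dose is held. The first reading has to supply a word such as previously. On the literal reading the resume list, which concerns drug-related events, need not collide with the note, and every rash that counts as dose-limiting is held. This is plausible, and it means the conflict is not certain. It does not remove the ambiguity: the note never says that it is limited to unrelated rash.

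A second reply is that general safeguards exist. The table is offered as guidelines. Section 5.5.1 and Section 7.6 let treatment stop for unacceptable toxicity or on the investigator's judgment. The end of Section 7.9 provides case-by-case review with the manufacturer's medical monitor. These make harm unlikely, but none says which rash rule governs.

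A third reply is that the patient numbers are mostly assumption, and this stands. The CA027-002 listing gives grade ranges by term, so a related Grade 3 event coded as rash should have changed the Grade 1 entry. An unlisted case would need a different term. Most of the data come from a nivolumab combination, not from this regimen.

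A reader might also infer that the note was simply meant to say Grade 2. The fatigue entries, which agree between the note and the resume list, point that way. So does the 7-day exception for Grade 3 rash, which would be largely redundant if such a rash were handled as Grade 1. But the pattern rests on one comparator, and on the literal reading the 7-day exception still has work to do for drug-related rash. The documents do not state the intent.

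**Conclusion.** The ambiguity is real and minor. On one natural reading the note permits infusion, with no hold, during a first Grade 3 rash, including a drug-related one. The Grade 3 row and the resume criteria do not permit that. On the other reading there is no conflict, and the text does not choose between them.

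It would go too far to say that the plan instructs staff to dose through a drug-related Grade 3 rash, or that Grade 2 is an established misprint.

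Few patients, probably none, would be affected. The calculation gives 0 to about 1 patient at Day 15, or 0.4 to 1.6 using the upper confidence limit. Both depend on the assumed rash duration and hospitalization, and on experience gathered mostly in combination with nivolumab. There is no effect on sample size, power, alpha or analysis.

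**What to change.** Delete the rash line from the table note, or limit it to Grade 3 rash not related to study drug. Any drug-related Grade 3 rash then follows the Grade 3 row and is held to Grade 1 or baseline. If the line is deleted, an unrelated Grade 3 rash follows that row too.

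Changing the note to Grade 2 skin toxicity is less attractive. It would move all Grade 2 skin events in these patients to the no-hold row, and so remove the table's present prompt to consider a hold when Grade 2 symptoms persist. Either of the two recommended changes keeps that prompt and leaves the existing resume bullet as it is.

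The cost is one line of wording and an occasional held Day 15 or optional Day 29 dose. Under the existing Grade 3 row, a rash that has not resolved by the next dose would lead to discontinuation.

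### Section 7.9 is inconsistent on skin toxicity: the dosing-table note says Grade 3 rash where the resume list, under the same condition, says Grade 2 skin toxicity

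*Combined protocol and SAP*

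**What the plan says.** All of this is in Section 7.9 of the protocol unless stated otherwise.

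- **Table, Grade 2 non-hematologic row.** The hold cell reads "Consider holding for persistent symptoms". Restart is at the same dose once the event is at Grade 1 or lower, or at baseline. The discontinuation cell names a toxicity that has not come down to "Grade 1 or baseline by the time of next treatment dose. Permanent discontinuation should be considered for any severe or life-threatening event".
- **Table, Grade 3 non-hematologic row.** Hold is mandatory. The restart and discontinuation cells match those of the Grade 2 row.
- **Table note.** Two exceptions are to be handled like Grade 1, which means no hold: Grade 2 fatigue, and "Grade 3 rash in patients who have not experienced a grade 3 drug-related skin AE".
- **Criteria to resume treatment.** The list repeats the Grade 1 or baseline threshold for restarting and then gives exceptions. For fatigue: "Participants may resume treatment in the presence of Grade 2 fatigue". For skin: "Participants who have not experienced a Grade 3 drug-related skin AE may resume treatment in the presence of Grade 2 skin toxicity". For the eye: "Participants with Grade 2 uveitis, episcleritis, iritis, eye pain, or blurred vision", leaving out those that "do not respond to topical therapy and does not improve to Grade 1 severity within the re-treatment period OR requires systemic treatment".
- **Exceptions to permanent discontinuation.** The skin entry is "Grade 3 pruritus or rash that returns to Grade 1 or baseline within 7 days with medical intervention".
- **Links to other text.** The resume list applies to events that do not meet the discontinuation criteria of Section 5.5. That section speaks of unacceptable toxicity judged with the investigator, and gives no grade. The closing paragraphs of Section 7.9 refer re-initiation to individual review by the investigator and the Sponsor.

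**The concern.** The table note and the resume list look like two copies of one exception list, yet they differ in the grade of skin event that they excuse. The note's version also sits awkwardly beside the Grade 3 row and the seven-day rule for Grade 3 rash. Because the note lacks the Grade 2 skin exception, a reader of the table alone sees persistent Grade 2 skin toxicity as a reason to stop. A reader of the resume list sees permission to dose.

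At stake are consistent dosing at day 15 or day 29 in the anti-IL-8 arm and, on one reading of the note, the handling of a Grade 3 rash. Section 7.9 governs dosing and not analysis, so the sample size, the error rate and the primary test are not involved.

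**Working it through.** The plan gives no figure on this point, so the check is mainly a comparison of texts.

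**1. Note against resume list, item by item.**

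| Item | Table note | Resume list |
|---|---|---|
| Fatigue | Grade 2 | Grade 2 |
| Skin, same condition in both (no Grade 3 drug-related skin event) | Grade 3 rash | Grade 2 skin toxicity |
| Eye | not listed | Grade 2, with limits |

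The fatigue items agree and the skin items share their condition. Only the grade and the term differ. That pattern suggests that Grade 3 in the note was meant to be Grade 2. This is an inference; no text says so.

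**2. The note as worded.** There are two readings.

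- *Plain wording.* A drug-related Grade 3 rash is itself a Grade 3 drug-related skin event, so the patient fails the note's condition and the Grade 3 row applies: hold. The note then covers only a Grade 3 rash that a physician judges unrelated to the drug (Section 8.2 leaves causality to a physician).
- *Condition read as no earlier Grade 3 skin event.* A first Grade 3 rash is handled like Grade 1 and dosed through. That contradicts the Grade 3 row and bypasses the seven-day rule.

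The Grade 2 skin exception is missing from the note on both readings.

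**3. A Grade 2 skin event still present at the next dose, with no Grade 3 drug-related skin event.** The table's discontinuation cell lists this as a stop criterion. The resume list permits dosing. Section 5.5 does not rank the two, and the exceptions to permanent discontinuation do not mention Grade 2 skin events. Individual review adds discretion without saying which rule governs.

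**4. A Grade 2 eye event that responds to topical therapy and needs no systemic treatment.** The table gives the same answer as in step 3. The resume list excepts the event only if its limit is read literally: non-response to topical therapy *and* no improvement to Grade 1 must both hold before the exception is lost. The bullet is a sentence fragment, so this half is less certain.

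**5. Size in doses.** Section 7.1 schedules doses on days 1, 15 and 29. The day 29 dose is optional and is for patients still in hospital with severe respiratory symptoms.

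- If the discontinuation cell operates only after a hold: the dose is held at day 15 and the event is still Grade 2 at day 29. Under the table the patient stops with 1 dose; under the list the patient may have 2. Difference: 2 − 1 = 1 dose.
- If the cell is applied literally at day 15: the table gives 1 dose and the list up to 3. Difference: at most 3 − 1 = 2 doses.

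**6. Size in patients.** Section 9.1.7 reports the combination study with nivolumab. Related rash is listed in 3 of 92 participants, 3/92 = 3.3%, all Grade 1. Grade 2 rash as listed is therefore 0/92.

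- Exact two-sided 95% upper limit: 1 − 0.025^(1/92) = 0.0393, or 3.9%.
- Applied to the anti-IL-8 arm, which also happens to number 92: 0.0393 × 92 = 3.6.

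The range is 0 to about 4 patients, before restricting to those still in hospital and still at Grade 2 on day 15 or day 29. The documents do not give that share. Section 9.1.7 lists only terms seen in more than 2 participants, so rarer skin terms would not appear. It names no eye event.

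**The case against.** The best defence is that the resume list presents itself as a set of exceptions to the same restart rule that the table states, and that the table is introduced as guidelines. A specific exception ordinarily qualifies a general rule. The Grade 2 row also only asks staff to consider a hold. If every event still at Grade 2 forced discontinuation, that discretion would be empty. So the restart and discontinuation cells are best read as following a hold, and a patient who was not held may be dosed under both texts. Permission to resume is also not an order to resume, re-initiation goes to individual review, and this is a single-center trial under one sponsor-investigator. Opposite decisions by different staff are therefore unlikely.

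Most of this stands, and it makes the point narrow. It does not remove it. Nothing ranks the list against the discontinuation column. The table carries its own exception note, so a reader of the table has little reason to look for a different list elsewhere. And none of these arguments explains why the note says Grade 3 rash.

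Two stronger readings are tempting. A reader might infer that the protocol lets a drug-related Grade 3 rash be dosed through. That requires reading the condition as no *earlier* Grade 3 event, a word that the note does not contain. A reader might also infer that table and list collide for every Grade 2 skin or eye event present at the next dose. The optional hold speaks against that, and the eye half depends on a literal conjunction in an incomplete sentence.

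**Conclusion.** The inconsistency on skin toxicity is real and lies in an operative dosing rule. The note's grade does not match the resume list under the identical condition, and it either defeats itself or conflicts with the Grade 3 row. Its omission of Grade 2 skin toxicity leaves the Grade 2 discontinuation cell unreconciled with the resume list. For topical-responsive Grade 2 eye events the same gap is arguable only.

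The effect is small. It concerns the day 15 or day 29 dose in the anti-IL-8 arm: one dose if the stop follows a hold, two at most otherwise. About 0 to 4 patients would be affected before the further restrictions. That range assumes that the rash rate listed for cancer patients on the nivolumab combination, across several dose levels, carries over to this population. Alpha, power and the primary analysis are unaffected. That the note contains a slip for Grade 2 is the likeliest explanation, but the documents do not confirm it.

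**What to change.** 1. In the table note, replace Grade 3 rash with Grade 2 skin toxicity and keep the existing condition. If Grade 3 is truly intended, reconcile it with the Grade 3 row's hold and the seven-day rule, and add the Grade 2 skin exception as well.
2. Add the Grade 2 eye exception to the note, with its limits on topical response and systemic treatment, written as a complete sentence in both places.
3. State that the Grade 2 fatigue, skin and eye exceptions override the restart and discontinuation cells of the Grade 2 non-hematologic row, and nothing else.

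Leave the Grade 3, Grade 4 and hematologic rows as they are. The override should not reach the exceptions to permanent discontinuation, which include short Grade 4 neutropenia. Nor should the amendment redefine when non-resolution triggers discontinuation. A general rule tied to held doses would also loosen the stop for Grade 3 and hematologic events unresolved at the next dose, and that is a separate clinical decision.

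The cost is a wording amendment, with no added visits, data or patients.
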